Study Significance: The large bony and soft tissue tumor resections performed in musculoskeletal oncologic patients presents the potential for significant blood loss. With basic arthroplasty being associated with significant intraoperative and postoperative blood loss often necessitating blood transfusion¹, larger bony resections with the use of endoprostheses presents an even higher risk². Transfusions themselves are not without known complications. Examples include infection, hemolytic transfusion reaction, and increased short-term mortality^{1,3}. Tranexamic acid (TXA), a synthetic analog of lysine, is an antifibrinolytic that is used to reduce blood loss. TXA works by blocking the lysine binding sites on plasminogen⁴. Perioperative use of TXA has been shown to decrease intraoperative and postoperative blood loss and decrease transfusion rates in both total knee arthroplasty and total hip arthroplasty⁵⁻¹⁵. It has also been shown to result in higher postoperative hemoglobin¹³. TXA also has been shown to decrease postoperative pain, swelling, length of hospital stay, and result in higher patient satisfaction¹⁶. The proposed research is intended to show if any correlation exists between administration of TXA or not to musculoskeletal oncology patients undergoing endoprosthetic reconstruction and perioperative blood loss and blood transfusion rates. The results of this study are

important because it will serve to fill the void in the current literature as there is no current literature available that has studied TXA administration in this specific patient population.

There have been several papers written with regards to the safety of TXA in high risk patients (i.e. previous PE/VTE event).^{21,22} Whiting et al showed that in high risk patients (defined as American Society of Anesthesiologists score of III or IV) , TXA was not associated with an increase in symptomatic thromboembolic events and was associated with a decrease in transfusion rates.²² Sabbag et al showed that patients with a history of VTE had a low risk of recurrent VTE (2%) after contemporary total hip arthroplasty and total hip arthroplasty, and that rate was not increased with the use of IV TXA.²¹

Literature Review

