This project has the potential to make a profound impact on how musculoskeletal oncology patients undergoing endoprosthetic reconstruction are managed in the perioperative period. This project will advance our knowledge in the musculoskeletal oncology field by potentially showing a significant correlation between administration of TXA and decreased rates of blood transfusions and perioperative blood loss. This has already been shown in the total joint arthroplasty literature. However, there is a lack of available literature that shows the effects of TXA on the patient population we wish to study. Because of this the use of TXA in this patient population is sporadic and varies widely from surgeon to surgeon. Providing a definitive answer regarding the safety and efficacy of TXA in this patient population would both unify the musculoskeletal oncology field in their use or abandonment of TXA, and potentially improve oncologic patient care in a similar fashion than that seen with the use of TXA in arthroplasty. The clinical outcomes that are evaluated by this project have the potential to make a profound impact on the lives of the patients we care for on a day-to-day basis.

This project has the potential to improve clinical outcomes of musculoskeletal oncology patients undergoing endoprosthetic reconstruction with TXA. Examples of potential improved clinical outcomes that could be derived from this project are: decreased intraoperative and postoperative blood loss and decreased transfusion rates with administration of TXA in this specific patient population.

II. Research Plan and Design

- A. Study Objectives:** Specific Aims: to determine if there is any significant difference in perioperative blood loss and blood transfusion rates when TXA is used compared to when it

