is not used in patients undergoing radical resection of bone and soft tissue sarcomas with endoprosthetic reconstruction. Statement of Purpose: to determine in a randomized controlled fashion if there is any difference in perioperative blood loss and blood transfusion rates following radial resection of malignant bony tumors with endoprosthetic reconstruction when TXA is used compared to when it is not. Primary outcome measure: determination of perioperative blood loss. To do this, values will be recorded preoperatively and compared to post-operative values. Perioperative blood loss will be calculated using the Hemoglobin balance method.²³⁻²⁶ Secondary outcome measures: (1) Blood transfusion rates. (2) Surgical drain output.

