
utilized. We also plan to record patient specific factors including age, sex, smoking status, BMI, pre-op diagnosis, operative time, comorbidities, and length of stay. These variables will be analyzed independently to detect any correlation with perioperative blood loss and erythrocyte transfusion rate.

C. Sample size, statistical methods, and power calculation

Method of Randomization: Patient randomization will be done via a randomization program through REDCap. The randomization process will be performed centrally at Kansas University Medical Center and the treating surgeon will not have access to the randomization list. Randomization will occur prior to definitive surgical procedure, and the treating surgeon and pharmacy will be notified to ensure adequate vials of tranexamic acid are available in the operating room (investigators/surgeons are not blinded). Patients will be blinded to treatment allocation. Treatment assignments will be stratified by type of resection. A power of 0.9 would require a total of 40 patients (20 per treatment group) be enrolled in the bony tumor group and 100 patients (50 per treatment group) in the soft tissue tumor group.

Since we are gathering entirely objective data the treating surgeon does not need to be blinded. Group differences in preoperative hemoglobin and hematocrit, transfusion requirements, drain output at 24 hours, and changes in hemoglobin and hematocrit will be compared using pairwise Student T-test analysis. Pairwise T-tests between each of the groups (for continuous variables) and Chi squared analysis (for categorical variables) will be used to determine if a statistically significant difference exists between the groups in terms of the patient specific factors that are also collected and analyzed (age, sex, smoking status, BMI, operative time, length of stay).

D. Subject Criteria (See Vulnerable Populations appendix, if applicable):

Inclusion criteria: Patients (male or female) between the ages of 18-90 undergoing wide resection of a malignant bony tumor of the lower extremity with endoprosthetic reconstruction or resection of soft tissue sarcoma measuring >5cm.

Exclusion criteria:

- Patients undergoing revision endoprosthetic reconstruction
- Patients with known coagulopathy
- Known history of DVT or embolic disease
- Benign tumors
- Patients with allergy to TXA
- Those refusing blood products
- Those concurrently on anti-coagulant therapy
- Pregnant and nursing women

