5. Timeline: Patients will be seen at routine post-operative visits at 2-3 weeks, 6 weeks, and 3 months where clinical examination and history taking will take place.

F. Risk/benefit assessment:

1. Physical risk: The primary concern with the use of TXA is the theoretical risk of developing a deep venous thrombosis. The patients will be monitored clinically for signs and symptoms of DVT while they are admitted to the hospital as well as at routine postoperative visits.
2. Psychological risk: We do not anticipate any psychologic risk to participants in this study.
3. Social risk: We do not anticipate any social risk in this study.
4. Economic risk: There will be no cost to subjects during this study, neither will there be any remuneration.
5. Potential benefit of participating in the study
 - a. to the individual subject and/or parent if any: None
 - b. to the population from which the subject is drawn: TXA in this patient population is sporadic and varies widely from surgeon to surgeon. Providing a definitive answer regarding the safety and efficacy of TXA in this patient population would both unify the musculoskeletal oncology field in their use or abandonment of TXA,

and potentially improve oncologic patient care in a similar fashion than that seen with the use of TXA in arthroplasty.

- c. to science, society, and humanity in general: A definitive answer regarding the safety and efficacy of TXA in this patient population would both unify the musculoskeletal oncology field in their use or abandonment of TXA

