2. Primary responsibility for the following activities, for example:
 - a. Determining eligibility: [name] MD, [name] MD, [name], MD
 - b. Obtaining informed consent: [name] MD, [name] MD, [name] MD
 - c. Providing on-going information to the study sponsor and the IRB: [name] MD, [name] MD, [name]
 - d. Maintaining participant's research records: [name] MD, [name] MD, [name]
 - e. Completing physical examination: [name] MD, [name] MD, [name] MD
 - f. Taking vital signs, height, weight: Clinical support staff for participating surgeons
 - g. Drawing / collecting laboratory specimens: Clinical support staff for participating surgeons
 - h. Performing / conducting tests, procedures, interventions, questionnaires: [name] MD, [name] MD, [name] MD

- i. Completing study data forms: [name] MD, [name] MD, [name] MD, [name] MD
- j. Managing study database: [name] MD, [name] MD, [name]

L. Assessment of Subject Safety and Development of a Data and Safety Monitoring Plan

1. Please note that any study proposal with more than minimal risk must include a data and safety monitoring plan. Elements of the plan include:
 - a. Persons/groups who will review the data (study team; independent safety monitor, data monitoring committee or formal DSMB) - Study team
 - i. An independent safety monitor will be used. [name], MD is an orthopaedic surgeon familiar with the use of TXA and uninvolved with the study in any other capacity.
 - b. Data/events that will be reviewed - Adverse events/complications arising in the participating patients.
 - c. Frequency of review: Review will occur every 4 months routinely. Additionally, a review will be conducted if 5 separate adverse events are reported prior to the scheduled bi-annual review.
 - d. Types of analyses to be performed – we will analyze the rate of complications (infections, PE, DVT) between the groups to make sure that we aren't getting statistically significant differences between groups
 - e. Safety-related triggers that would cause the PI to stop or alter the study – If our analysis of complications reveals a statistically significant difference between groups, we will place the study on hold until an appropriate remedy can be reached. We will consult with the IRB before resuming the study. If no remedy can be determined the study will be permanently held

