1. Describe steps to be taken to assure that the data collected are accurate, consistent, complete and reliable. (source data verification, audits or self – assessment) Source data verification and self-audits will be performed. The protocol for the clinical trial will be spelled out for the participants. A discussion will be had between the PI at KUMC and the PI at the participating institution to ensure the protocol is understood.

V. Data Analysis and Reporting

A. Statistical and Data Analysis: Group differences in preoperative hemoglobin and hematocrit, transfusion requirements, drain output at 24 hours, difference in hemoglobin balance method, and changes in hemoglobin and hematocrit will be compared using pairwise Student T-test analysis. Pairwise T-tests between each of the groups (for continuous

variables) and Chi squared analysis (for categorical variables) will be used to determine if a statistically significant difference exists between the groups in terms of the patient specific factors that are also collected and analyzed (age, sex, smoking status, BMI, operative time, length of stay, presence of coagulopathy, specific anticoagulation regimen should it differ from study protocol, size of resection, depth of resection, location of tumor, pathologic diagnosis, stage of disease).

B. Outcome: We expect the results to be similar to the TXA arthroplasty studies/literature with regards to decreased perioperative blood loss and decreased transfusion rates. There are not necessarily any criteria for success or failure. The results of this study will help provide a definitive answer regarding the safety and efficacy of TXA in oncologic patients. This will help unify the musculoskeletal oncology field in their use or abandonment of TXA.

C. Study results to participants: The study results/conclusions will not be given to subjects unless they are specifically asked for at future scheduled outpatient clinic visits. Once the proposed study is completed a conversation with subjects can occur on an outpatient basis at their routine scheduled clinic visits regarding our results and conclusions if desired. The subjects reserve the right to know what conclusions were drawn from the study they directly participated in. In addition, we plan to publish a manuscript with our results/conclusions after completion of the study which can be sought after if desired.

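### The plan promises a definitive answer on TXA safety, but thrombosis and infection are not among the study outcomes or the planned final analysis, and 70 patients per arm leaves large differences open

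*Combined protocol and SAP*

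**What the plan says.** The safety claim appears in three sections. I.C (Rationale) and II.F (Risk/benefit assessment, under benefits to the population) both speak of "Providing a definitive answer regarding the safety and efficacy of TXA in this patient population", and say that it would settle whether the field uses or abandons TXA. II.F repeats the claim under benefits to science and society. V.B (Outcome) softens it: "The results of this study will help provide a definitive answer regarding the safety and efficacy of TXA in oncologic patients".

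II.A names perioperative blood loss as the primary outcome and continues: "Secondary outcome measures: (1) Blood transfusion rates. (2) Surgical drain output". V.A lists hemoglobin and hematocrit measures, transfusion, drain output, the hemoglobin balance result and patient factors. It lists no complication.

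Complications are compared between groups in one place, the data and safety monitoring plan (II.L). Rates of infection, PE and DVT are analysed to "make sure that we aren't getting statistically significant differences between groups", and a significant difference puts the study on hold. II.B and II.F describe clinical surveillance for DVT or embolism in hospital and at follow-up visits, with Doppler only if there are symptoms. The last routine visit is at 3 months (II.E).

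**The concern.** II.F calls DVT the primary concern with TXA, and the plan offers its safety conclusion as a basis for practice in cancer patients. Nothing in the planned final analysis would produce that conclusion. The only safety comparison is a monitoring check that asks whether a difference is statistically significant, with no interval, margin, event definition, time window or power.

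When events are few, a non-significant difference is the likely result whether or not TXA raises the risk. If the report then rests on the absence of significance, a trial that could not have seen a doubled thrombosis risk might be cited as showing that TXA is safe.

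**Working it through.** **Inputs from the plan.** Section II.C sizes the soft tissue stratum at 50 per arm and the bone stratum at 20 per arm, both for a power of 0.9. Pooled across strata, 20 + 50 = 70 per arm. The safety events are those in II.L.

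**Inputs that had to be assumed.** Alpha is not stated; two-sided 0.05 is used. No thrombosis rate is given for this population. The only VTE figure, 2% in I.B, is for recurrence in arthroplasty patients with prior VTE, whom II.D excludes. A range of control rates from 1% to 10% is used instead. No test is named for complications. Fisher's exact test and uncorrected chi-squared are both shown; chi-squared is the only categorical test in the plan, named for patient factors.

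**The plan's own figure.** The power of 0.9 cannot be reproduced, because no endpoint, alpha, effect or SD is given. If it refers to a difference in means, the standardised difference is d = (1.960 + 1.282) × √(2/n), which is 1.02 at n = 20 and 0.65 at n = 50. No power is given for safety.

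**Power for complications at 70 per arm.** Power is the sum of Bin(i; 70, pC) × Bin(j; 70, pT) over all pairs of event counts (i, j) whose test gives p ≤ 0.05.

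| Control rate | Doubled: Fisher | Doubled: chi-squared | Tripled: Fisher | Tripled: chi-squared |
|---|---|---|---|---|
| 1% | 0.1% | 3% | 1% | 8% |
| 2% | 2% | 9% | 8% | 21% |
| 5% | 11% | 20% | 41% | 52% |
| 10% | 30% | 38% | 81% | 86% |

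For 80% power to detect a doubling, the usual two-proportion formula, n = [1.960 × √(2p̄(1 − p̄)) + 0.842 × √(pC(1 − pC) + pT(1 − pT))]² / (pT − pC)² with p̄ the mean of the two rates, gives 2,319, 1,141, 435 and 199 per arm at control rates of 1%, 2%, 5% and 10%.

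**What counts as significant.** Against 0 control events, Fisher needs 6 TXA events (p = 0.028; 5 events give p = 0.058). Against 1 control event it needs 8 of 70, or 11.4% (p = 0.033; 7 events give p = 0.063). Chi-squared needs 7 against 1.

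**What a null result leaves open.**
- With 0 of 70 TXA patients affected, the exact two-sided 95% upper limit is 1 − 0.025^(1/70) = 5.1%.
- With 0 v 0 events, the Newcombe 95% limits for the risk difference are ±z²/(n + z²) = ±3.84/73.84 = ±5.2 points.
- With 1 v 1 events the Newcombe limits are ±6.3 points; with 3 v 3, ±8.1 points.
- By stratum, 0 v 0 events give ±3.84/53.84 = ±7.1 points in soft tissue (50 per arm) and ±3.84/23.84 = ±16.1 points in bone (20 per arm).

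Fewer than 70 per arm may be analysed, since II.B excludes patients given non-standard TXA dosing and the plan makes no allowance for losses. That would widen these intervals.

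**The case against.** The strongest reply is that the claim of a definitive answer sits in rationale, benefit and outlook text. The aims and hypotheses concern blood loss, transfusion and drain output only, V.B claims only to help, and V.B also says there are not necessarily criteria for success or failure. The significance check in II.L is a trigger for pausing the study, not a final decision rule. All of that stands, and it limits the point to what the trial can be said to show.

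Four stronger readings are tempting, and the documents do not support them.
- A reader might infer that no safety outcome is named at all. II.L names infection, PE and DVT, compares them between groups and provides an independent safety monitor. What is missing is their place among the outcomes and in V.A.
- A reader might infer that the plan commits to treating non-significance as proof of safety. No section says so; the risk is that it could be read that way.
- A reader might infer that a null result is almost certain even if TXA triples the risk. That is fair at control rates of 1% to 2% using Fisher, but not at 5% (power 41% to 52%) or 10% (81% to 86%).
- A reader might take the 2% in I.B as the expected control rate. It comes from a population that this trial excludes.

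The choice of test also matters: at 2% v 6%, chi-squared gives 21% where Fisher gives 8%. It does not change the conclusion for a doubling, where neither test exceeds 38% anywhere in the assumed range.

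**Conclusion.** The point holds in this form: the plan says that the trial will supply, or help supply, a definitive safety answer, and the design does not have that property. Safety events are monitored but are outside the stated outcomes and the final analysis, and their only comparison is a significance check. Power to detect a doubled risk is at most 30% (Fisher) or 38% (chi-squared) over control rates of 1% to 10%, and even a trial with no events is compatible with an excess of about 5 percentage points. A null result could be over-read.

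The power figures rest on an assumed two-sided alpha of 0.05 and assumed control rates. The interval widths need only 70 analysed patients per arm and the 95% level. The efficacy analyses are unaffected.

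**What to change.** 1. In I.C, II.F and V.B, replace the promise of a definitive answer on safety with an estimate of safety.
2. In II.A and V.A, list symptomatic DVT/PE and infection through the 3-month visit as a safety outcome, with definitions. Report TXA against no TXA as a risk difference with a 95% interval suited to rare events (for example Newcombe), overall (70 v 70) and by stratum (50 v 50 and 20 v 20).
3. State in V.A that a non-significant difference will not be interpreted as evidence of safety.

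The pooling and the interval method are reporting choices; another interval that behaves well with few events would serve. The events are already monitored, so no extra patients, tests or visits are needed. The cost is one extra table and a less favourable stated claim.

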APPENDIX I: VULNERABLE POPULATIONS

- I.** The recruitment plan will not include any of the groups noted below.
- II. Cognitively or decisionally impaired individuals:** N/A. Cognitively or decisionally impaired individuals will be excluded from this study.
- III. Children:** N/A. Children will be excluded from this study.
- IV. Pregnant women:** N/A. Pregnant women will be excluded from this study.
- V. Prisoners:** N/A. Prisoners will be excluded from this study.
- VI. Students and/or Employees:** N/A. Students and/or Employees at KUMC will be excluded from this study.
